In the first three months (the Observation phase) of this proof-of-concept study, a telemedicine center for the PACU will monitor patients assigned to two PACU bays. Both the telemedicine center and nurses caring for patients in the PACU bays will separately document physiological derangements (Table 2), treatable symptoms (Table 3), or a situation requiring urgent medical intervention (telemedicine center only; Table 4) during the PACU stay. Clinicians in the telemedicine center will assess when the patient meets discharge criteria, based on the modified Aldrete scale¹⁵ and their clinical judgment. They will document the time that discharge criteria are met, the modified Aldrete scale score at this time, and any additional relevant information. If clinicians in the telemedicine center judge that they are unable to determine a patient's readiness for discharge, they will document their reasons (Table 5). Clinical judgment will be used in determining appropriate discharge parameters for patients with pre-existing conditions. The telemedicine center clinicians will document each patient's information outlined in Tables 2-5 directly into REDCapTM (a secure web application for managing online surveys and databases) and AlertWatch. After a patient has been discharged from the PACU, the PACU nurse will fill out a form providing information outlined in Tables 2-5. This includes

information on physiological derangements, treatable symptoms, and discharge information. This form will be collected by the research team, and the information in the form will be documented in REDCap. During this phase of the study, clinicians in the telemedicine center will not communicate with clinicians in the PACU (nurses or physicians), unless there is a patient safety event.

Table 2. Physiological derangements and complications

Did the patient have any of the following physiological derangements:	Definition: (for study purposes)
Persistent confusion / delirium	
Tachycardia	HR >120/min
Bradycardia	HR <45/min
New onset atrial fibrillation	
Respiratory depression	<8 respirations per minute
Hypoxemia	<90% O ₂ Saturation
Hypotension	MAP <55
Weakness	<5/5 power in limbs
Emesis / vomiting	
Hyperglycemia	Glucose >200mg/dL
Hypothermia	Temperature < 35.5 C
Low urine output (for PACU stay >4h)	<0.5 ml/kg per hour

Table 3. Symptoms requiring treatment

Did the patient complain of the following symptoms:	
Dizziness or lightheadedness	Difficulty breathing
Nausea	Shivering

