Physiological derangements – Success will be measured (in the observation phase) by the ability of the telemedicine center clinicians to identify physiological derangements as they are occurring in the PACU. The extent to which the telemedicine center clinicians can identify these physiological derangements will be measured by comparing PACU nurse and telemedicine center assessment surveys for each patient (Figure 3).

Symptom identification and management – Success will be measured (in the observation phase) by the ability of the telemedicine center clinicians to identify treatable symptoms as they arise in the PACU. The extent to which the telemedicine center clinicians can identify these treatable symptoms will be measured by comparing PACU nurse and telemedicine center assessment surveys for each patient (Figure 3).

Emergency situations – Success will be measured (in the observation phase) by the ability of the telemedicine center clinicians to identify situations requiring emergency medical intervention as they are occurring in the PACU. By construction, any time the telemedicine center feels that an emergency situation is present, preserving patient safety mandates contacting the bedside clinician.

During each such contact, the telemedicine center clinician will ask if the PACU nurse was already aware of the situation, disagreed with the assessment, and had already spoken to the supervising physician regarding it. The occurrence of emergency medical situations will be extracted from the electronic health record, and the agreement between telemedicine center and PACU nurse assessments will be quantitated.

PACU discharge – Success will be measured by the ability of the telemedicine center clinicians to identify when patients are ready for discharge (observation phase [without communication] and interaction phase [active communication with patient and PACU clinicians]) (Figure 3). The impact of the telemedicine center on this key function will be examined based on feedback from key stakeholder focus groups (interaction phase; see *Aim 2*). The difference between sign-out times in the observation and the interaction phases will be compared.

Data collection methods and measures during the interaction phase

Aim 1: Demonstrate the potential utility of a telemedicine center for the PACU, to assist with PACU functions

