The accuracy of physiologic, symptom, and status assessments is less straightforward to analyze. At the heart of the proposal is the belief that telemedicine assistance will detect some abnormalities not caught (or caught later) by the bedside team and detect that the patient has adequate status for PACU discharge before the bedside nurse. Using the bedside assessment as a gold standard is therefore limited. Similarly, although we believe that abnormalities detected by either bedside or telemedicine are unlikely to be false positives, we have no way of assuring that. We also cannot reliably determine the timing of the bedside nurse's detection of an abnormality, as they may document it much later if they believe it does not require an immediate intervention.

Each status assessment event can occur multiple times for each patient; however, we are unlikely to accurately capture the bedside nurse's impression of the number of times an event occurred. We will therefore binarize the presence of each assessment type and display confusion matrices (count tabulations) for each assessment type, which we will summarize with Jaccard indices. The "null hypothesis" that these measures do not agree at all is not meaningful or the subject of this study. As described above, neither is a directional superiority hypothesis possible to evaluate. Final Aldrete scores will be assessed with pearson correlation, and a t-test of the difference in scores presented. Differences in ready-for-discharge times will be summarized as mean and standard deviation, with the null hypothesis of zero mean tested by t-test with a robust standard error.

Agreement of emergency medical status is unlikely to have enough events to be statistically compared. We will present cross-tabulations of (emergency detected by telemedicine center:

yes/no) and (PACU nurse: disagree, investigate and agree, already aware, physician contacted). The absolute rate of telemedicine center false positives (team disagrees), true positives (team unaware), true positives (team aware), and false negatives (team aware > 15 minutes prior or t never detects) will be presented with 95% confidence intervals.

Data Collection

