Multiple sources will be utilized for data collection from which outcome measures will be extracted. Data from AlertWatch will be automatically logged to a secure database. Preoperative patient characteristics, comorbidities, surgical and clinical history, as well as perianesthesia information will be captured using Epic Systems software (Verona, WI, USA). Prospective data will be collected from Epic Systems for the datapoints mentioned throughout the proof-of-concept study.

Relevant PACU information outlined in Tables 2-5 for patients in this study will be collected and entered into a REDCap database managed by Washington University. Data will not be shared with others outside the research team.

Methodological strengths and limitations

A strength of this study is its pragmatic approach as a real-world study with measurable aims. Feasibility will be determined, and information will be provided regarding logistical implications of establishing a telemedicine solution for the PACU. Many telemedicine solutions have been implemented without considering barriers and facilitators, such as cultural and political obstacles. This study proactively addresses these concerns, which might facilitate future successful implementation and generalization of similar telemedicine initiatives. Specific

functions of the PACU have been detailed, and the methods of this study will allow assessment of the ability of the telemedicine center to facilitate the accomplishment of these functions. This study also has important limitations. First, as a proof-of-concept, it will only include two PACU bays. Thus, its applicability to a large PACU will not be resolved. Second, PACU clinicians will be aware of the initiative, which could modify their behavior during the conduct of the study. Third, as the study design is observational with a before and after approach, improvements (for example in time to discharge) cannot be causally attributed to the intervention; there could be confounding explanations. Fourth, the current discharge criteria for the PACU do not have a firm evidential foundation (there is no gold standard measure for discharge readiness), and clinician gestalt plays an important role. This limitation can be addressed through development of rigorous, reliable and practical criteria. Finally, as a single center study, results will not necessarily be broadly generalizable.

Adverse Events and Safety Monitoring

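### A Table 2 or 3 item left off the nurse's post-discharge form is tabulated as telemedicine-only, and no step checks the blank against the chart

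*Combined protocol and SAP*

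**What the plan says.** The Observation Phase section describes two routes for the same items. For telemedicine: "The telemedicine center clinicians will document each patient's information outlined in Tables 2-5 directly into" REDCap and AlertWatch. For the bedside: "After a patient has been discharged from the PACU, the PACU nurse will fill out a form providing information outlined in Tables 2-5". The form then passes through the study team: "This form will be collected by the research team, and the information in the form will be documented in REDCap".

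The same section opens with a sentence that fits poorly with a post-discharge form: "Both the telemedicine center and nurses caring for patients in the PACU bays will separately document physiological derangements (Table 2), treatable symptoms (Table 3") and urgent situations (telemedicine only), and it places this documentation within the PACU stay. No bedside study instrument completed during the stay is described.

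The success measures for physiological derangements and for symptoms, listed at the end of the Interaction Phase section, apply to the observation phase and rest on "comparing PACU nurse and telemedicine center assessment surveys for each patient". Under Secondary Outcomes each item is coded present or absent, shown as a confusion matrix and summarized by a Jaccard index. That section also gives the belief behind the project, that "telemedicine assistance will detect some abnormalities not caught (or caught later) by the bedside team".

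The section on the primary intervention lists the EHR among the sources that feed the telemedicine center. For outcomes, the EHR is named as the source for emergency events. The Data Collection section adds more generally: "Prospective data will be collected from Epic Systems for the datapoints mentioned throughout the proof-of-concept study". It is not named as a check on the nurse's Table 2 and Table 3 answers.

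**The concern.** The two sides of each table are not recorded on equal terms. The bedside entry depends on a form completed once the patient has gone and then transcribed. The telemedicine entry is direct and is made by clinicians who also receive EHR information. A nurse could chart nausea, telemedicine could see that entry and record it, and the nurse could leave the item blank on the later form. The patient would be tabulated as detected by telemedicine only, although the bedside record came first.

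Secondary Outcomes anticipates two weaknesses of the bedside record, late documentation and poor event counts, and binary coding answers the second. Neither the text nor the coding deals with an item that was noticed but not ticked. Two things are at stake: the Jaccard index, which is the planned summary of agreement, and the telemedicine-only count, which a reader is likely to set beside the stated belief about abnormalities the bedside does not catch.

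**Working it through.** The documents give no event rate, omission rate or expected Jaccard index, so there is no figure of the plan's own to reproduce. The check is a cell-by-cell calculation with assumed values.

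**Inputs**
- Observation-phase patients: 250 (Study Size).
- Assumed: prevalence of an item, 10% (20% as a second case); share f of nurse-detected items left off the form, 5%, 10% or 20%; no false positives; detection by the two teams independent given an event.

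**Formulas**
- Events E = 250 × prevalence.
- With telemedicine detection a, nurse detection b, and nurse-form yes s = b(1 − f): both = E·a·s; telemedicine-only = E·a·(1 − s); nurse-only = E·(1 − a)·s.
- Jaccard = both / (both + telemedicine-only + nurse-only).

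**Case 1: both teams detect every event (a = b = 1).** Nurse-only is zero and Jaccard = 1 − f at any prevalence. The true index is 1.00.

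| f | Jaccard | Telemedicine-only, E = 25 (10%) | Telemedicine-only, E = 50 (20%) |
|---|---|---|---|
| 5% | 0.95 | 1.25 | 2.5 |
| 10% | 0.90 | 2.5 | 5 |
| 20% | 0.80 | 5 | 10 |

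Every patient in the last two columns was detected at the bedside.

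**Case 2: each team detects 90% (a = b = 0.9), E = 25.**
- f = 0: both = 25 × 0.9 × 0.9 = 20.25; telemedicine-only = 25 × 0.9 × 0.1 = 2.25; nurse-only = 25 × 0.1 × 0.9 = 2.25; Jaccard = 20.25 / 24.75 = 0.82.
- f = 20%: s = 0.72; both = 25 × 0.9 × 0.72 = 16.2; telemedicine-only = 25 × 0.9 × 0.28 = 6.3; nurse-only = 25 × 0.1 × 0.72 = 1.8; Jaccard = 16.2 / 24.3 = 0.67.

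Two equally good teams, with an even 2.25 to 2.25 split, would appear as 6.3 to 1.8. Independence is doubtful here because telemedicine receives EHR information, so Case 2 shows the direction of the shift and does not forecast its size.

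**Direction.** An omission for an event telemedicine recorded moves the patient from both to telemedicine-only. An omission for an event telemedicine did not record moves the patient from nurse-only to neither. In both cases the bedside is under-credited.

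**The case against.** The strongest reply is that the plan makes no claim this could bias. It tests no hypothesis on these tables, says that directional superiority cannot be evaluated, calls the bedside a limited gold standard, and uses a symmetric index. A reader might infer that the plan scores bedside misses, or that omission biases the study's result in favor of telemedicine. The documents do not support either. In both cases worked above, omission lowers the pre-specified Jaccard index, which makes telemedicine look worse on the planned measure of success. The apparent advantage arises only if someone reads the telemedicine-only cell in the light of the background belief.

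A reader might also infer that nurses answer from memory while telemedicine records in real time. The documents do not say so. The nurse may consult the chart, direct entry describes a route and not a time, and one sentence has both teams documenting during the stay. Telemedicine clinicians can omit items too.

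These points limit the concern but do not remove it. Whatever the nurse consults, a blank on the form is final, and nothing in the plan separates an item not noticed from one not reported.

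It is also fair to object to redefining bedside detection as a tick, any note or any treatment. That would enlarge the bedside side alone and need adjudication, and a treatment does not establish the item: an analgesic does not show pain above 7/10, and an antiemetic may be preventive. The fix is therefore a supplement limited to structured fields.

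**Conclusion.** The concern holds for the Table 2 and Table 3 comparisons in the observation phase. The form-based tables cannot distinguish bedside non-detection from non-reporting, and the plan acknowledges unreliable timing and counts but not omission. The consequence is a lower Jaccard index and a telemedicine-only cell that invites misreading. The size is unknown. The illustration of 0.95 to 0.80 instead of 1.00 rests on assumed omission of 5% to 20%, complete detection by both teams and no false positives.

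The reach is limited to descriptive secondary tables. Emergency situations are outside this point, because they use the EHR and the nurse's answer at the time of contact. Even so, the comparison is the stated success measure for Aims 1a and 1b, and no other analysis in the plan would expose the problem.

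**What to change.** 1. In the Observation Phase section, reconcile the two statements on when nurses document, and say what the nurse may consult when completing the form.
2. In the success measures and under Secondary Outcomes, keep the form-versus-telemedicine tables and label the telemedicine-only cell as not reported on the nurse form.
3. Pre-specify a second set of confusion matrices and Jaccard indices in which a nurse-no becomes yes when a structured, nurse-entered EHR field from the stay records that item, for example a pain score above 7/10, or charted nausea, emesis, shivering or itching. Do not count automatically filed monitor values, or treatment alone, as bedside detection.
4. State that telemedicine-only counts will be interpreted only after this cross-check, and add omission to the listed limitations of the bedside record.

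The cost is one EHR query for about 250 observation-phase patients, from a source the study already uses. The documents do not say whether nurse-entered and automatically filed values can be separated, so this should be confirmed first. Charting is itself imperfect, and late charting means the check shows whether an item was noted, not when. The supplement applies to the bedside side only, so both versions must be shown.

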Severe pain (Numerical Rating Scale >7/10)	Itching
Chest pain unrelated to surgery	

Table 4. Emergency medical interventions

Did the telemedicine center contact PACU clinicians for any of the following interventions:	
Intubation	Unplanned transfusion
Assisted ventilation	Naloxone administration
Cardiopulmonary resuscitation	Return to OR
Cardioversion	Other (free text box)
If Yes, please check all that apply:	
 PACU nurse already aware of the situation	
 PACU nurse unaware of the situation	
 PACU nurse disagreed with the assessment	
 PACU nurse had already spoken to the supervising physician regarding the situation	

Other (please describe):

*Only the telemedicine center will document the detection of urgent situations.

Table 5. Patient discharge readiness

At what time did the patient sufficiently recover to be discharged (case attending anesthesiologist contacted for discharge)?	
PACU Nurses	Telemedicine Center for PACU
Time anesthesiologist is contacted for discharge evaluation	Time ready for discharge
Aldrete Score at discharge	Aldrete Score at discharge
	Unable to determine patient's readiness for discharge
Modified Aldrete Scale Component and Scoring Parameters	If Unable to fully assess, select reason(s) why (Checkbox)
Respiration	 More patient information needed  Equipment issues  Patient cooperation  Other (free text box)
2 – Able to take deep breath and cough	
1 – Dyspnea / Shallow Breathing	
0 – Apnea	
O₂ Saturation	
2 – Maintains > 92% on room air	
1 – Needs O ₂ inhalation to maintain O ₂ saturation > 90%	
0 – Saturation <90% even with supplemental O ₂	
Consciousness	
2 – Fully awake	
1 – Arousable on calling	
0 – Not responding	
Circulation	
2 – BP ± 20mmHg pre-op	
1 – BP ± 20-50mmHg pre-op	
0 – BP ± greater than 50mmHg pre-op	
Motor Activity	
2 – Able to move 4 extremities voluntarily or on command	
1 – Able to move 2 extremities voluntarily or on command	
0 – Able to move 0 extremities voluntarily or on command	

Interaction Phase (3 months)

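### Observation-phase safety contacts can move an item that telemedicine saw before the nurse into the both-yes cell, because contact records are not linked to Table 2 and Table 3 items

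*Combined protocol and SAP*

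**What the plan says.** Under Observation Phase (3 months), the two teams document Table 2 derangements and Table 3 symptoms separately, and "clinicians in the telemedicine center will not communicate with clinicians in the PACU (nurses or physicians), unless there is a patient safety event". The safety event is not defined. The Emergency situations paragraph makes contact compulsory in one case: "any time the telemedicine center feels that an emergency situation is present, preserving patient safety mandates contacting the bedside clinician".

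The nurse's record comes later: "After a patient has been discharged from the PACU, the PACU nurse will fill out a form providing information outlined in Tables 2-5". Table 2 asks "Did the patient have any of the following physiological derangements", and Table 3 asks whether the patient complained of each listed symptom. Neither asks who noticed the item, or when.

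For Aims 1a and 1b, the extent of telemedicine's detection in the observation phase is "measured by comparing PACU nurse and telemedicine center assessment surveys for each patient". Secondary Outcomes then reduces each assessment type to present or absent, cross-tabulates the two raters, and summarizes each table with a Jaccard index.

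Contacts go into Table 4, which only telemedicine completes and which asks "Did the telemedicine center contact PACU clinicians for any of the following interventions". The options are interventions such as intubation or naloxone, plus free text. One tick box reads "PACU nurse unaware of the situation", and for emergencies the plan adds: "During each such contact, the telemedicine center clinician will ask if the PACU nurse was already aware of the situation". Secondary Outcomes uses these awareness answers to classify emergency detections, and nowhere else.

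**The concern.** The nurse's form is meant to supply the second of two separate assessments. Once telemedicine has told an unaware nurse about an item, the nurse's later yes for that item is partly telemedicine's own finding. The entry then moves from the telemedicine-only cell to the both-yes cell, and the contact itself cannot move it the other way.

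This matters because Secondary Outcomes puts at the center of the project the belief that telemedicine will find abnormalities which the bedside team misses or finds later. The telemedicine-only cell is where that would show. Contact is likeliest for the more severe items, where added detection is of most interest. A reader of the tables could not tell which agreements followed a call.

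**Working it through.** The plan gives no figure for this analysis: no event rate, contact rate or expected Jaccard index. Its only power statement concerns time to discharge readiness and does not use these tables. There is therefore nothing to reproduce. The check is a trace of one entry, then an illustration on assumed counts.

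**Trace of one entry**

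1. Telemedicine sees saturation below 90% (hypoxemia in Table 2) before the nurse does, and records yes.
2. It judges this a safety event and calls. The Table 4 record shows that the nurse was unaware.
3. After discharge the nurse completes the form. The patient did have hypoxemia, so yes is the correct answer.
4. The patient enters the both-yes cell for hypoxemia. Without the call, and if the nurse had found neither this episode nor another, the patient would be in the telemedicine-only cell.
5. The contact record can be matched to the patient, since the data are held in REDCap. But a patient may have several Table 2 or 3 items, and the record names an intervention or free text. No rule carries it into the hypoxemia table.

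**Arithmetic**

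For one item type, let a = both, b = nurse only and c = telemedicine only, as the counts would stand with no contacts. Let k = telemedicine-only patients converted to both-yes after a contact, and u = both-yes patients recorded as contacted with the nurse unaware.

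- Recorded Jaccard = (a + k)/(a + b + c)
- Sensitivity Jaccard, scoring the nurse no for the u patients = (a + k − u)/(a + b + c)
- Telemedicine-only share of telemedicine's yes answers = (c − k)/(a + c)

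All counts below are assumptions.

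| a, b, c | Case | Recorded | Sensitivity | Telemedicine-only share |
|---|---|---|---|---|
| 20, 5, 10 | No contacts, or 3 contacts with the nurse already aware (k = u = 0) | 20/35 = 0.571 | 20/35 = 0.571 | 10/30 = 33% |
| 20, 5, 10 | k = u = 1 | 21/35 = 0.600 | 20/35 = 0.571 | 9/30 = 30% |
| 20, 5, 10 | k = u = 3 (upper illustration) | 23/35 = 0.657 | 20/35 = 0.571 | 7/30 = 23% |
| 5, 2, 3 | Rare item, k = u = 1 | 6/10 = 0.600 | 5/10 = 0.500 | 2/8 = 25% (3/8 = 38% without contact) |

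Each converted patient adds 1/(a + b + c) to the index: 1/35 = 0.029 in the first setting and 1/10 = 0.100 in the rare one.

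**What the sensitivity value can and cannot say**

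Take k = 3 with counts 20, 5, 10.

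- If the nurse would later have found one of the three unprompted, agreement without contact would have been 21/35 = 0.600. The sensitivity value of 0.571 lies below it.
- If one of the three was wrongly recorded as aware, then u = 2 and the sensitivity value is 21/35 = 0.600. It lies above the no-contact 0.571.

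The sensitivity value can therefore fall on either side of the no-contact value.

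**The case against.** The case for leaving the plan alone has five parts.

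- **The nurse's yes is correct.** The form asks whether the item occurred, and it did. The plan treats the bedside assessment as a limited reference, says that no directional superiority hypothesis can be evaluated, and tests nothing on these tables. Telemedicine's own yes is unchanged. This stands, and it means that no stated figure is wrong. But the plan does not mention its own contacts as a reason why entries may move between cells.
- **Table 4 already captures awareness.** For emergencies, true positives are to be reported by whether the team was aware, with confidence intervals. This stands in part. What remains missing is the link to the Table 2 or 3 item and a rule for showing it.
- **Few entries will be affected.** The plan expects too few emergencies for statistical comparison. Items such as itching or shivering would seldom be safety events. The Introduction says that nurses typically have at most two patients in the initial phase. An affected item must reach safety level, be unknown to the nurse at contact, not be found in another episode, and then be ticked. This stands.
- **Uncontacted agreement is not shown to be independent either.** Under Primary Intervention, telemedicine receives EHR data, so bedside charting can inform telemedicine's yes without any call. This stands, and it limits what a sensitivity value may claim.
- **Questions about each item would burden a safety call.** This stands, so the remedy should add none.

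**Conclusion.** The gap is real and minor. An item that telemedicine finds first and communicates can be counted as both-yes, and the planned tables do not show when this has happened. The distortion from contact runs one way: it raises recorded agreement and shrinks the telemedicine-only cell. Its size is unknown. It is zero if nurses were already aware at every contact, and probably small otherwise. Primary outcome results and planned tests do not depend on it.

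A reader might infer two stronger things that the documents do not support.

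- *That nurse charting can never settle who was first, because it may be late.* Secondary Outcomes gives late charting as a reason only for abnormalities that the nurse thinks need no immediate intervention. The items at issue here have reached safety level. For emergencies, the plan itself uses a timing criterion of more than 15 minutes' prior awareness. Its general caution about the timing of nurse detection remains, but this point does not need it.
- *That rescoring contacted items recovers independent agreement, or bounds it from below.* The awareness answer is recorded by one of the two raters and concerns the situation, not the item. The nurse might have found the item later. The EHR route also leaves the rest of the both-yes cell open to influence in the other direction.

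**What to change.** 1. After each observation-phase contact, the telemedicine clinician tags on the existing Table 4 record which Table 2 or 3 item or items prompted it. The single awareness answer already on that record is used; no question is added to the call.
2. In Secondary Outcomes, keep the as-recorded table and Jaccard index for each item type. Alongside, show how many both-yes entries were contacted with the nurse unaware.
3. If there are any, add one sensitivity Jaccard that scores the nurse no for those entries. Describe it as a sensitivity value for contact-prompted agreement only, not as an estimate of, or bound on, independent agreement, and give the reasons: one rater records awareness, at the level of the situation; the nurse might have found the item later; and telemedicine sees bedside charting.

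Do not exclude contacted items.

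The cost is one extra field on an existing record and a few table rows. It needs no extra patients, visits or nurse forms, and the safety contact is unchanged.
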